11.9. Safety Endpoints and Analyses

Safety assessments will include the examination of the incidence rates of AEs, vital signs, laboratory parameters, and physical examinations. Safety analyses will be conducted on the safety analysis set, which is defined as all subjects who have received at least a 1 dose of study agent.

Adverse Events

The verbatim terms used in the CRF by investigators to identify AEs will be coded using the Medical Dictionary for Regulatory Activities (MedDRA). Treatment-emergent AEs are AEs with onset during the treatment period or that are a consequence of a pre-existing condition that has worsened since baseline. All reported treatment-emergent AEs will be included in the analysis. For each AE, the percentage of subjects who experience at least 1 occurrence of the given event will be summarized by system organ class and preferred term for treatment group. Treatment-emergent AEs will also be summarized by a maximum severity and relationship to study agent. Separate summaries will be provided for SAEs and AEs leading to study agent discontinuation.

In addition, summary tables will be presented by treatment group for each of the endpoints within each specified period:

Double-Blind Period:

- a. Proportion of subjects with treatment-emergent AEs and severe AEs through Weeks 52 and 104.
- b. Proportion of subjects with study agent injection site reactions through Week 52.
- c. Proportion of subjects with severe infections through Weeks 52 and 104.
- d. Open-Label Extension Period:
 1. Continue to evaluate safety and exploratory efficacy endpoints as per the [Time and Events Schedule](#) (open-label extension period) and no new efficacy hypotheses will be tested compared to the double-blind period.

Listings, datasets, or subject narratives may be provided, as appropriate, for those subjects who die, who discontinue treatment due to an AE, or who experience a severe or an SAE.

Clinical Laboratory Tests

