12.1. Definitions

12.1.1. Adverse Event Definitions and Classifications

Adverse Event

An AE is any untoward medical occurrence in a clinical study subject administered a medicinal (investigational or non-investigational) product. An AE does not necessarily have a causal

relationship with the treatment. An AE can therefore be any unfavorable and unintended sign (including an abnormal finding), symptom, or disease temporally associated with the use of a medicinal (investigational or non-investigational) product, whether or not related to that medicinal (investigational or non-investigational) product. (Definition per International Conference on Harmonisation [ICH])

This includes any occurrence that is new in onset or aggravated in severity or frequency from the baseline condition, or abnormal results of diagnostic procedures, including laboratory test abnormalities.

Note: The sponsor collects AEs starting with the signing of the ICF (refer to Section 12.4.1, All Adverse Events, for time of last AE recording).

Serious Adverse Event

An SAE based on ICH and European Guidelines on Pharmacovigilance for Medicinal Products for Human Use is any untoward medical occurrence that at any dose:

- Results in death.
- Is life-threatening (The subject was at risk of death at the time of the event. It does not refer to an event that hypothetically might have caused death if it were more severe.)
- Requires inpatient hospitalization or prolongation of existing hospitalization.
- Results in persistent or significant disability/incapacity.
- Is a congenital anomaly/birth defect.
- Is a suspected transmission of any infectious agent via a medicinal product.
- Is Medically Important.*
- *Medical and scientific judgment should be exercised in deciding whether expedited reporting is also appropriate in other situations, such as important medical events that may not be immediately life-threatening or result in death or hospitalization but may jeopardize the subject or may require intervention to prevent one of the other outcomes listed in the definition above. These should usually be considered serious.
- Unlisted (Unexpected) Adverse Event/Reference Safety Information.

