12.4. Procedures

12.4.1. All Adverse Events

All AEs and special reporting situations, whether serious or non-serious, will be reported from the time a signed and dated ICF is obtained until completion of the subject's last study-related procedure, which may include contact for follow-up of safety. Serious adverse events, including those spontaneously reported to the investigator within 52 weeks after the last dose of study agent (which is the end of the study), must be reported using the Serious Adverse Event Form. In

addition, SAEs will be requested to be submitted for subjects who withdraw early from the study for a year after their last study agent dose. The sponsor will evaluate any safety information that is spontaneously reported by an investigator beyond the time frame specified in the protocol.

All events that meet the definition of an SAE will be reported as SAEs, regardless of whether they are protocol-specific assessments. Anticipated events will be recorded and reported as described in [Attachment 6](#).

All AEs, regardless of seriousness, severity, or presumed relationship to study agent or device, must be recorded using medical terminology in the source document and the CRF. Whenever possible, diagnoses should be given when signs and symptoms are due to a common etiology (eg, cough, runny nose, sneezing, sore throat, and head congestion should be reported as "upper respiratory infection"). Investigators must record in the CRF their opinion concerning the relationship of the AE to study therapy. All measures required for AE management must be recorded in the source document and reported according to sponsor instructions.

All devices associated with device-related AEs will be investigated including the return of the device to the sponsor for inspection.

The sponsor assumes responsibility for appropriate reporting of AEs to the regulatory authorities. The sponsor will also report to the investigator (and the head of the investigational institute where required) all suspected unexpected serious adverse reactions (SUSARs). The investigator (or sponsor where required) must report SUSARs to the appropriate Independent Ethics Committee/Institutional Review Board (IEC/IRB) that approved the protocol unless otherwise required and documented by the IEC/IRB. A SUSAR will be reported to regulatory authorities unblinded. Participating investigators and IEC/IRB will receive a blinded SUSAR summary, unless otherwise specified.

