6.1. Adverse Events

The verbatim terms used in the CRF by investigators to identify adverse events will be coded using the Medical Dictionary for Regulatory Activities (MedDRA). Any AE starting at or after the initial administration of study agent through the end of the trial is considered to be treatment emergent. If the event occurs on the day of the initial administration of study agent, and either event time or time of administration are missing, then the event will be assumed to be treatment emergent. If the event date is recorded as partial or completely missing, then the event will be

considered to be treatment emergent unless it is known to be prior to the first administration of study agent based on partial onset date or resolution date.

All reported treatment-emergent adverse events will be included in the analysis. Treatment-emergent adverse events (TEAEs) by system organ class and preferred term (ie, number and proportion of subjects with one or more TEAEs within a system organ class) will be summarized by treatment group.

The following TEAE summary tables will be provided:

- Any TEAEs
- TEAEs by severity
- Serious treatment-emergent adverse event (SAEs)
- Reasonably related TEAEs
- Frequent TEAEs
- TEAEs leading to study agent discontinuation
- Injection site reactions
- TEAEs of special interest such as hypoglycemia events, infections, tuberculosis, malignancies

These summary tables will provide the count and percentage of subjects with 1 or more of the specified AEs by treatment group, and by system-organ class/preferred term respectively.

In order to support the additional assessment of particular categories of adverse events, additional summary is done on selected adverse events. The number and percent of subjects with the following selected TEAEs will be summarized by treatment group:

In addition to the summary tables, listings of subjects with the following AEs will be provided:

- Death
- Serious TEAEs
- TEAEs leading to discontinuation of study agent
- Hypoglycemia episodes reported as TEAEs
- Key Safety findings including malignancies, opportunistic infections, a new autoimmune disease or worsening of an existing autoimmune disease, and so forth.

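### SAP 6.1 omits the protocol's worsening route to treatment-emergent status, so an adverse event held as one record with a pre-dose start that worsens after dosing would be left out of the AE tables and the serious-event listing

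*Protocol*

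**What the plan says.** Protocol 11.9 gives two routes to treatment-emergent status, joined by an or: "AEs with onset during the treatment period or that are a consequence of a pre-existing condition that has worsened since baseline". The proportion of subjects with treatment-emergent AEs is a secondary safety endpoint (Protocol 2.1 and 9.2.3).

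SAP 6.1 gives one route: "Any AE starting at or after the initial administration of study agent through the end of the trial is considered to be treatment emergent". Its rule for partial or missing dates also turns on the start alone. Such an event is "considered to be treatment emergent unless it is known to be prior to the first administration of study agent". The SAP has no worsening clause and gives no reason for leaving it out.

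The flag controls most of the AE output. The tables are introduced with "The following TEAE summary tables will be provided", and the listing of serious events is headed "Serious TEAEs".

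On recording, Protocol 12.1.1 states "The sponsor collects AEs starting with the signing of the ICF". The same section counts an aggravation from the baseline condition as an AE occurrence.

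**The concern.** The two documents use one term for two different sets of events. Protocol section 11 leaves the specific details to the SAP, but here the SAP narrows a definition that the protocol has already fixed, and that definition determines a named endpoint. Two programmers, one working from each document, could report different counts for it.

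At stake is an event that begins between consent and first dose and then becomes more severe or serious on study agent. The protocol's second route exists to count such an event. Serious and severe events may be few in a trial of 81 subjects, so whether one is counted can be visible in the table.

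**Working it through.** No figure in the plan needs reproducing. The check compares the definitions, follows a record through each, and sorts the safety outputs by whether they use the flag.

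**1. Can the affected records exist?** Yes. AE collection starts at consent (Protocol 12.1.1 and 12.4.1), and screening may run up to 28 days before dosing (Protocol 9.1.2). AEs with a known pre-dose start can therefore be in the database.

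**2. Follow one event through both rules.** Take an AE that starts in screening as mild and becomes severe or serious after first dose.

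| How the worsening is recorded | Protocol 11.9 | SAP 6.1 |
|---|---|---|
| Original record updated, pre-dose start kept | Treatment-emergent (worsening route) | Not treatment-emergent |
| New record, start date is the date of worsening | Treatment-emergent | Treatment-emergent |

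The documents disagree only in the first row. Neither says which row applies. Protocol 17.6 refers to CRF completion guidelines, which are not part of these documents.

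**3. Which outputs depend on the flag?**

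- Limited to treatment-emergent events by SAP 6.1: the AE summary tables (any, by severity, serious, related, frequent, leading to discontinuation, injection site, special interest) and the "Serious TEAEs" listing. The listings for discontinuation and for hypoglycemia reported as AEs are worded the same way. Injection site reactions follow an injection, so that table is not affected in practice.
- Not worded as treatment-emergent only: the death listing and the listing of "Key Safety findings including malignancies, opportunistic infections, a new autoimmune disease or worsening of an existing autoimmune disease, and so forth" in SAP 6.1.
- Not based on the AE flag at all: laboratory summaries, shift tables and toxicity grades (SAP 6.2), and vital signs (SAP 6.3).

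**4. Scale.** The planned arms are 54 golimumab and 27 placebo (Protocol 11.2, SAP 1.4).

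- One golimumab subject: 100 × 1/54 = 1.9 percentage points.
- One placebo subject: 100 × 1/27 = 3.7 percentage points.

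A proportion moves only if the lost event was that subject's sole qualifying event for the row. That is less likely for any TEAE than for the severe, serious or single-preferred-term rows. The documents give no rate of screening-onset AEs or of their worsening, so the number affected cannot be estimated.

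**The case against.** The strongest reply is that Protocol 12.1.1 already makes an aggravation from baseline an AE in its own right. If sites enter it with the date of worsening, it passes the SAP's start-date test and nothing is lost. This stands, and it makes the loss conditional. It does not remove the conflict, because capture then rests on a recording convention that neither document states. The protocol's clause does not depend on that convention.

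Several stronger readings are tempting, and the documents do not support them:

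- **That such an event disappears from every safety output.** It does not. Laboratory and vital-sign outputs do not use the flag, and the death and key-safety listings are not worded as limited by it. SAEs also go to the sponsor within 24 hours (Protocol 12.4.2) and to the DMC on an ongoing basis (Protocol 9.6). Protocol 11.9 permits listings or narratives for severe events and SAEs, though only as an option.
- **That Protocol 12.4.1 steers sites to a single record.** Its sentence, "Whenever possible, diagnoses should be given when signs and symptoms are due to a common etiology", is about naming a diagnosis instead of its separate symptoms. It does not address severity changes or start dates.
- **That the typical case is an infection already present at first dose.** Active infection is an exclusion (Protocol 4.2.1, criterion 9), and eligibility is reviewed again at Week 0 (Protocol 9.1.3.1). An unrecognised infection, or an EBV or CMV load below the exclusion threshold without clinical infection, remains possible. So does any non-infectious screening AE.
- **That the loss falls mainly on golimumab.** With 2:1 allocation, equal per-subject rates lose twice as many golimumab subjects from twice the denominator, so the expected change in the proportions is the same. Randomization should balance events that began before treatment. A difference between arms requires the drug to cause worsening, and the documents give no rate for that.

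It is also fair that SAP section 6 plans no formal safety comparison, so no test result changes.

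**Conclusion.** The point holds as a conflict between protocol and SAP on the definition behind a secondary safety endpoint. An AE kept as one record with a known pre-dose start, and more severe or serious after dosing, is counted by the protocol and omitted from the SAP's AE summary tables and its serious-event listing.

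This rests on one assumption that the documents neither confirm nor exclude: that at least some worsenings are held under the original record. Frequency and any imbalance between arms are unknown. The size is known only per subject: 1.9 points on golimumab or 3.7 on placebo, at the planned arm sizes and when no other event qualifies the subject. A reader should not infer a wholesale loss of safety information or a bias in favour of golimumab. The point is worth correcting because the omission is unexplained and cheap to close.

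**What to change.** In SAP 6.1, restore the protocol's worsening clause: an AE with onset before the first dose that increases in severity or becomes serious on or after the first dose is treatment-emergent, dated from the worsening. Apply it only where the record shows higher severity or seriousness after dosing.

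Do not add a default that treats a missing severity-change date as worsening. An AE that never changed has no such date, so that default would turn stable baseline conditions into treatment-emergent events.

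Separately, list all SAEs that occur or become serious after first dose, whatever their TEAE flag. This protects the most important events even where the CRF does not hold the history of severity.

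The cost is one sentence in the SAP, a programming flag, one wider listing and possibly slightly higher TEAE counts. The documents do not show that severity-change dates are collected, so the team should check what the CRF holds before programming.

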11.10. Interim Analysis

An interim analysis using the 4-hour C-peptide AUC in response to a MMTT will be planned for the study. The primary goal of this analysis will be to obtain an early examination of the treatment effect to facilitate the planning of future studies. It is anticipated that the interim analysis will take place after at least 60% of subjects complete their Week 26 4-hour, MMTT assessment. All available 4-hour, C-peptide AUC data at interim analysis will be incorporated in this analysis. No formal DBL is planned for this interim analysis.

An IAC will be established to review the interim data and formulate recommendations in accordance with the objectives of the interim analysis. The IAC will consist of at least a clinician and a statistician (neither of whom are involved in the conduct of the study or compound development), one of whom will chair the committee, and other members as required based on the results of the interim analysis. Details will be provided in the IAC charter. The DMC serves the IAC function. The disclosure of unblinded results will be limited to specific sponsor personnel not involved in the study. Interim analyses results will not be disseminated to investigators or individuals associated with the conduct of the study. The interim analyses will not have any statistical impact on the analyses of any other endpoints.

11.11. Data Monitoring Committee

An Independent DMC consisting of external experts and internal experts not associated with this study will be established to monitor data on an ongoing basis to ensure the continuing safety of the subjects enrolled in this study. The committee will meet periodically to review interim data. After the review, the DMC will make recommendations regarding the continuation of the study. The details will be provided in a separate DMC charter.

The DMC will consist of at least one medical expert in the relevant therapeutic area and at least one statistician. The DMC responsibilities, authorities, and procedures will be documented in its charter.

12. ADVERSE EVENT REPORTING

Timely, accurate, and complete reporting and analysis of safety information from clinical studies are crucial for the protection of subjects, investigators, and the sponsor, and are mandated by regulatory agencies worldwide. The sponsor has established Standard Operating Procedures in conformity with regulatory requirements worldwide to ensure appropriate reporting of safety information; all clinical studies conducted by the sponsor or its affiliates will be conducted in accordance with those procedures.

12.1. Definitions

12.1.1. Adverse Event Definitions and Classifications

Adverse Event

An AE is any untoward medical occurrence in a clinical study subject administered a medicinal (investigational or non-investigational) product. An AE does not necessarily have a causal

relationship with the treatment. An AE can therefore be any unfavorable and unintended sign (including an abnormal finding), symptom, or disease temporally associated with the use of a medicinal (investigational or non-investigational) product, whether or not related to that medicinal (investigational or non-investigational) product. (Definition per International Conference on Harmonisation [ICH])

This includes any occurrence that is new in onset or aggravated in severity or frequency from the baseline condition, or abnormal results of diagnostic procedures, including laboratory test abnormalities.

Note: The sponsor collects AEs starting with the signing of the ICF (refer to Section 12.4.1, All Adverse Events, for time of last AE recording).

Serious Adverse Event

An SAE based on ICH and European Guidelines on Pharmacovigilance for Medicinal Products for Human Use is any untoward medical occurrence that at any dose:

- Results in death.
- Is life-threatening (The subject was at risk of death at the time of the event. It does not refer to an event that hypothetically might have caused death if it were more severe.)
- Requires inpatient hospitalization or prolongation of existing hospitalization.
- Results in persistent or significant disability/incapacity.
- Is a congenital anomaly/birth defect.
- Is a suspected transmission of any infectious agent via a medicinal product.
- Is Medically Important.*
- *Medical and scientific judgment should be exercised in deciding whether expedited reporting is also appropriate in other situations, such as important medical events that may not be immediately life-threatening or result in death or hospitalization but may jeopardize the subject or may require intervention to prevent one of the other outcomes listed in the definition above. These should usually be considered serious.
- Unlisted (Unexpected) Adverse Event/Reference Safety Information.
- An AE is considered unlisted if the nature or severity is not consistent with the applicable product reference safety information. For golimumab, the expectedness of an AE will be determined by whether or not it is listed in the Investigator's Brochure. For exogenous insulin with a marketing authorization, the expectedness of an AE will be determined by whether or not it is listed in the package insert/summary of product characteristics.
- Adverse Event Attribution Definitions.
- The following provides guidance on how the study team is to assess and categorize the relationship of AEs in relation to study agent:

Adverse Event Association With The Study Agent

- **Not Related:** An AE that is not related to the use of the drug.
- **Doubtful:** An AE for which an alternative explanation is more likely, eg, concomitant drug(s), concomitant disease(s), or the relationship in time suggests that a causal relationship is unlikely.
- **Possible:** An AE that might be due to the use of the drug. An alternative explanation, eg, concomitant drug(s), concomitant disease(s), is inconclusive. The relationship in time is reasonable; therefore, the causal relationship cannot be excluded.
- **Probable:** An AE that might be due to the use of the drug. The relationship in time is suggestive (eg, confirmed by dechallenge). An alternative explanation is less likely, eg, concomitant drug(s), concomitant disease(s).
- **Very Likely:** An AE that is listed as a possible adverse reaction and cannot be reasonably explained by an alternative explanation, eg, concomitant drug(s), concomitant disease(s). The relationship in time is very suggestive (eg, it is confirmed by dechallenge and rechallenge).

This study will utilize sponsor-supplied study agent dosing devices, the PFS-U and VarioJect as detailed in the SIPPM. The following provides guidance on how the study team is to assess and categorize the relationship of AEs in relation to these devices.

Adverse Event Association With The Study Device

- **Not related:** There is another obvious cause of the AE other than the study device.
- **Unlikely:** There is another more likely cause of the AE other than the study device.
- **Possibly:** The AE could be due to the study device.
- **Probably:** The AE is probably attributable to the study device.
- **Definitely:** The AE is most likely or definitely attributable to the study device.

